## **Definition of Terms**

**Life threatening:** An AE is life threatening if the patient was at immediate risk of death from the event as it occurred; i.e., it does not include a reaction that if it had occurred in a more serious form might have caused death. For example, drug-induced hepatitis that resolved without evidence of hepatic failure would not be considered life-threatening even though drug-induced hepatitis can be fatal.

**Hospitalization:** In general, hospitalization signifies that the patient has been detained (usually involving at least an overnight stay) at the hospital or emergency ward for observation and/or treatment that would not have been appropriate in the physician's office or outpatient setting. When in doubt as to whether 'hospitalization' occurred or was necessary, the AE should be considered serious. Hospitalization for elective surgery or routine clinical procedures that are not the result of AE (e.g., elective surgery for a pre-existing condition that has not worsened) need not be considered AEs or SAEs. If anything untoward is reported during the procedure, that occurrence must be reported as an AE, either 'serious' or 'non-serious' according to the usual criteria.

**Disability/permanent damage:** An AE is disabling or caused permanent damage if it resulted in a substantial disruption of a person's ability to conduct normal life functions, e.g., a significant, persistent or permanent change, impairment, damage or disruption in body function/structure, physical activities and/or quality of life.

**Adverse Event of Special Interest (AESI):** AESIs are of scientific and medical interest specific to understanding of the Investigational Product and may require close monitoring and rapid communication by the investigator to the sponsor. An AESI may be serious or non-serious. The rapid reporting of AESIs allows ongoing surveillance of these events in order to characterize and understand them in association with the use of this investigational product.

**Immune-related Adverse Events (irAE):** An irAE is defined as an adverse event that is associated with drug exposure and is consistent with an immune-mediated mechanism of action and where there is no clear alternate aetiology. Serologic, immunologic, and histologic (biopsy) data, as appropriate, should be used to support an irAE diagnosis. Appropriate efforts should be made to rule out neoplastic, infectious, metabolic, toxin, or other etiologic causes of the irAE.

### **8.3.2 Exposure During Pregnancy**

Exposure during pregnancy (i.e., exposure in-utero [EIU]) may occur in a female study participant, the female partner of a male study participant or study site personnel working with the investigational product (e.g., occupational exposure) if:

- A female becomes or is found to be pregnant during treatment or within 6 months after discontinuing treatment or having been directly exposed to the investigational product;

- A male is exposed to the investigational product prior to or around the time of conception or during the pregnancy of his partner.

If exposure in-utero occurs, the investigator must submit an SAE form and an EIU Supplemental Form within 24 hours of awareness of the exposure, regardless of whether an AE or SAE has occurred.

In the event of pregnancy in a female study participant, if the pregnancy is continued, study treatment will be immediately discontinued.

In the event of exposure of the pregnant partner of a male study participant, the study participant should be asked to deliver an EIU Pregnant Partner Release of Information Form to his partner. The Investigator must document on the EIU Form that the patient was given this letter to provide to his partner.

Follow-up to obtain pregnancy outcome information is to be conducted for all EIU reports. In the case of a live birth, the health of the neonate should be assessed at the time of birth and for up to 3 months after birth. Further follow-up of birth outcomes will be handled on a case-by-case basis (e.g., follow-up on preterm infants to identify developmental delays). In the event the pregnancy is terminated, the reason(s) for termination should be reported and, if clinically possible, the structural integrity of the terminated fetus should be assessed by gross visual inspection.

If the outcome of the pregnancy meets the criteria for an SAE (i.e., ectopic pregnancy, spontaneous abortion, intrauterine fetal demise, neonatal death, or congenital anomaly), an SAE report should be submitted to the Sponsor.

### **8.3.3 Adverse Events of Special Interest**

#### **8.3.3.1 Durvalumab Adverse Events of Special Interest**

AESIs for durvalumab include but are not limited to events with a potential inflammatory or immune-mediated mechanism and which may require more frequent monitoring and/or interventions such as steroids, immunosuppressants and/or hormone replacement therapy. These AESIs are being closely monitored in clinical studies with durvalumab monotherapy and combination therapy.

If the Investigator has any questions in regards to an adverse event (AE) being an irAE, the Investigator should promptly contact the Study Sponsor.

AESIs observed with durvalumab include:

- Colitis
- Pneumonitis

- ALT/AST increases / hepatitis / hepatotoxicity
- Neuropathy / neuromuscular toxicity (i.e. events of encephalitis, peripheral motor and sensory neuropathies, Guillain-Barré, and myasthenia gravis)
- Endocrinopathy (i.e. events of hypophysitis, adrenal insufficiency, and hyper- and hypothyroidism)
- Dermatitis
- Nephritis
- Pancreatitis (or labs suggestive of pancreatitis - increased serum lipase , increased serum amylase)

### **8.3.3.2 Mocetinostat Adverse Event of Special Interest**

All pericardial findings, regardless of seriousness and relationship to study medication, should be reported to the Sponsor with the use of the “Pericardial Event Report Form” provided by the Sponsor, according to the procedures for SAE expedited reporting (see [Section 8.4.2](#)). When reporting pericardial events, available ECHO results/reports (or other means of diagnosis if available) should also be provided, for review by the Medical Monitor.

## **8.4 Reporting of SAEs and AEs**

### **8.4.1 Reporting Period**

The active reporting period for SAEs begins from the time that the patient provides informed consent (i.e., prior to undergoing any study-specific procedure or assessment) and continues until 90 days post last administration of either therapy. All SAEs will be followed until the event has resolved or stabilized to a chronic condition, whichever is later. Death must be reported if it occurs during the active reporting period for SAEs regardless of whether a subsequent anticancer therapy is administered. Serious adverse events occurring to a patient after the active reporting period has ended should be reported to the Sponsor if the investigator becomes aware of them and if the investigator assesses at least a reasonable possibility of being related to study drug.

The reporting period for non-serious AEs begins from the day of first dose of study treatment and continues until at least 28 days after last administration of study treatment and/or until recovery from all acute toxicities associated with the drug administration to a chronic condition, whichever is later. If a patient begins a subsequent anticancer therapy, the AE reporting period ends at the time the new treatment is started.

### **8.4.2 Reporting Requirements**

All SAEs must be reported within 24 hours of Investigator/site knowledge of the event, irrespective of the extent of available AE information, by faxing the SAE report to the Sponsor's pharmacovigilance representative designated in the Study Manual. The 24-hour timeframe also applies to additional new information (follow-up) on previously forwarded SAE reports and to the initial and follow-up reporting of exposure during pregnancy and exposure via breastfeeding. The need for an expedited report to regulatory authorities will be determined by the Sponsor and necessary reporting will be performed by the Sponsor. The Sponsor will notify study investigators of all Suspected, Unexpected (as judged against the Investigator Brochure) Serious Adverse Reaction (SUSAR) reports. The investigator is responsible for reporting all SUSARs to the IRB/EC.

All AE (including SAEs) must be documented in source documents and reported in the CRF. Please note that the CRF and SAE report forms may collect information in somewhat different formats. Where the requested data overlap in different formats, the information should be consistent between the two forms.

## **9 STATISTICS**

Detailed methodology for summary and statistical analyses of the data collected in this study will be documented in a [Statistical Analysis Plan \(SAP\)](#), which will be maintained by the Sponsor. The SAP may modify the plans outlined in the protocol; however, any major modifications of the primary endpoint definition and/or its analysis will also be reflected in a protocol amendment.

### **9.1 Hypothesis and Sample Size**

#### **9.1.1 Phase 1**

Approximately 24 patients may be enrolled into the Phase 1 portion of the study and up to 261 patients will be enrolled into the Phase 2 portion. Precise sample size cannot be defined, as it is dependent on the number of dose escalations based on the mTPI method, and the number of patients enrolled in the expansion cohorts.

The mTPI method ([Ji-2013](#)) will be employed in decision making concerning dose escalation within each regimen investigated. The assumptions to be applied in establishing the mTPI methodology are:

- each specific regimen exploration will include up to 30 patients;
- the MTD is defined to have 0.25 probability of toxicity; and

- the acceptable variance around the MTD is  $\pm 0.05$  (i.e., the region of the MTD is 20% to 30% incidence of dose limiting toxicity).

### **9.1.2 Phase 2**

The 4-cohort Phase 2 portion uses sample sizes based on Predictive Probability Design (Lee-2008). ORR in accordance with RECIST 1.1 is the primary clinical benefit endpoint. In creating the statistical designs, the Type 1 error ( $\alpha$ ) is constrained to  $<0.05$  and Power ( $1-\beta$ ) is constrained to  $\geq 0.90$ .

#### **Statistical Design Applied to Phase 2 Cohorts 1, 3 and 4**

The ORR using a PD-L1 inhibitor in the population with advanced NSCLC having no or low PD-L1 expression, or prior disease progression on a checkpoint inhibitor, is assumed to be 5% ( $p_0$ ); thus this rate is considered uninteresting. The target ORR using mocetinostat in combination with durvalumab in this study is 30% ( $p_1$ ). Stage 1 of enrollment will include a minimum of 9 evaluable patients. With exactly 9 evaluable patients at Stage 1, if at least 1 patient has an Objective Response, 8 additional evaluable patients will be enrolled, for a total sample size of 17 evaluable patients. If at least 3 Objective Responses are observed, further investigation may be warranted. If the true ORR is 5% (null hypothesis), the probability of early termination during the study is 0.63; the Type 1 error is equal to 0.0466 and the power is equal to 0.9045.

#### **Statistical Design Applied to Phase 2 Cohort 2**

The ORR using a PD-L1 inhibitor in the population with advanced NSCLC having high PD-L1 expression is assumed to be 27% ( $p_0$ ); thus this rate is considered uninteresting. The target ORR using mocetinostat in combination with durvalumab in this study is 50% ( $p_1$ ). Stage 1 of enrollment will include approximately 17 evaluable patients. With exactly 17 evaluable patients at Stage 1, if at least 5 patients have Objective Responses, 27 additional evaluable patients will be enrolled, for a total sample size of 44 evaluable patients. If at least 18 Objective Responses are observed, further investigation may be warranted. If the true ORR is 27% (null hypothesis), the probability of early termination during the study is 0.50; the Type 1 error is equal to 0.0303 and the power is equal to 0.9018.

The exact stopping rules for all cohorts will be calculated based on the Predictive Probability Design, once the exact number of patients evaluable at Stage 1 is known. The aim is to get about 9 evaluable patients at Stage 1 for cohorts 1, 3 and 4 and about 17 evaluable patients at Stage 1 for cohort 2.

If Stage 2 results in Cohorts 3 and 4 are of high interest for efficacy, enrollment may be expanded to as many as 100 patients total in each cohort to narrow the 95% Confidence Interval (CI) around the ORR point estimate. Table 14 presents estimates of the 95% CI around the observed ORR for several potential outcomes using the sample size of 100 patients, and the Clopper-Pearson method.

**Table 14: Estimates of 95% CI Using Clopper-Pearson in After Enrollment of 100 Patients**

Number of Observed Responses Among 100 Patients	ORR	95% CI
25	25%	16.9-34.7%
30	30%	21.2-40.0%
35	35%	25.7-45.2%
40	40%	30.3-50.3%
50	50%	39.8-60.2%

## 9.2 Data Handling

Listings of all patient data will be prepared. Data summaries will be presented in tabular and/or graphical format and summarized descriptively, where appropriate. Details of planned analyses will be described in the [SAP](#).

For all variables, only the observed data from patients will be used in the statistical analyses; there is no plan to estimate missing data. Patients without a valid clinical response assessment will be assigned a best overall response of not evaluable (NE). Data from patients who are lost to follow-up or have missing observations before reaching an endpoint in any of the time-to-event analyses will be treated as censored with specific rules defined in the SAP.

## 9.3 Analysis Populations

### 9.3.1 *Modified Intent-to-Treat Population*

The Modified Intent-to-Treat (mITT) population is defined as all patients who receive treatment with both mocetinostat and durvalumab on this study.

The primary efficacy analyses of the primary and secondary efficacy endpoints will be performed in the mITT population. In addition, the mITT population will be used in making decisions to expand the study to the next stage of enrollment (to up to 100 patients).

### 9.3.2 *Clinical Activity Evaluable Population*

In order to be considered eligible for the clinical activity evaluable population, the patient must have at least one on-study disease assessment or discontinue from treatment for PD. Patients who discontinue treatment prior to the first on-study disease assessment for an AE, toxicity, or withdraw consent are considered non-evaluable for disease assessment and will not be part of the clinical activity evaluable population.

This population will be used to present tumor responses as well as to make decision on the Predictive Probability design.

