## LIST OF ABBREVIATIONS

ADA	Anti-drug Antibodies
AE	Adverse Event
ALT	Alanine Aminotransferase
APC	Antigen Presenting Cells
AST	Aspartate Aminotransferase
AUC	Area Under the Curve
CBR	Clinical Benefit Rate
CFR	Code of Federal Regulations
CI	Confidence Interval
C max	Maximum Plasma Concentration
CR	Complete Response
CRF	Case Report Form
CRO	Contract Research Organization
CT	Computed Tomography Scan
CTA	Clinical Trial Application
CTCAE	Common Terminology Criteria for Adverse Events
DCR	Disease Control Rate
DLT	Dose Limiting Toxicity
DNA	Deoxyribonucleic Acid
DR	Duration of Response
EC	Ethics Committee
ECG	Electrocardiogram
ECOG	Eastern Cooperative Oncology Group
EIU	Exposure In-Utero
FDA	Food and Drug Administration
GCP	Good Clinical Practice
GLP	Good Laboratory Practice
HDAC	Histone Deacetylases
HDACi	Histone Deacetylase Inhibitor
HDPE	High-Density Polyethylene
HLA	Human Leukocyte Antigen
IB	Investigator's Brochure

ICF	Informed Consent Form
ICH	International Conference on Harmonization
IND	Investigational New Drug
INR	International Normalized Ration
irAE	Immune-related Adverse Event
IRB	Institutional Review Board
IUD	Intrauterine Device
IV	Intravenous
MAb	Monoclonal Antibody
MDSC	Myeloid-derived Suppressor Cell
MDSCs	Myeloid-Derived Suppressor Cells
MedDRA	Medical Dictionary for Regulatory Activities
mg	Milligram
MHC	Major Histocompatibility Complex
mITT	Modified Intent-to-Treat
mL	Milliliter
MRI	Magnetic Resonance Imaging
MTD	Maximum Tolerated Dose
mTPI	Modified Toxicity Probability Interval
NCI	National Cancer Institute
NE	Not Evaluable
NK	Natural Killer
NSCLC	Non-Small Cell Lung Cancer
ORR	Objective Response Rate
OS	Overall Survival
PCR	Polymerase Chain Reaction
PD	Objective Progression of Disease
PD-1	Programmed Cell Death 1
PD-L1	Programmed Cell Death Ligand 1
PET	Positron Emission Tomography
PFS	Progression-Free Survival
PK	Pharmacokinetics
PR	Partial Response
PTT	Partial Thromboplastin Time

QTc	Corrected QT Interval
RECIST	Response Evaluation Criteria in Solid Tumors
SAE	Serious Adverse Event
SAP	Statistical Analysis Plan
SD	Stable Disease
SOC	Standard of Care
TAA	Tumor Associated Antigens
TIW	Three Times Weekly
Treg	T Regulatory Cells
ULN	Upper Limit of Normal
WBC	White Blood Cell
WOCBP	Women of Child Bearing Potential

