### **1.3.5 Durvalumab Monotherapy Clinical Activity in Solid Tumor Diseases**

In Study CD-ON-durvalumab-1108, 456 of 694 subjects treated with durvalumab 10 mg/kg Q2W were evaluable for response (defined as having  $\geq 24$  weeks follow-up, measurable disease at baseline, and  $\geq 1$  follow-up scan, or discontinued due to disease progression or death without any follow-up scan). In PD-L1 unselected patients, the objective response rate (ORR), based on investigator assessment per Response Evaluation Criteria in Solid Tumors (RECIST) v1.1, ranged from 0% in uveal melanoma (n = 23) to 20.0% in bladder cancer (n = 15), and disease control rate at 24 weeks (DCR-24w) ranged from 4.2% in triple-negative breast cancer (TNBC; n = 24) to 39.1% in advanced cutaneous melanoma (n = 23). PD-L1 status was known for 383 of the 456 response evaluable subjects. Across the PD-L1-positive tumors, ORR was highest for bladder cancer, advanced cutaneous melanoma, hepatocellular carcinoma (HCC; n = 3 each, 33.3% each), NSCLC (n = 86, 26.7%), and squamous cell carcinoma of the head and neck (SCCHN; n = 22, 18.2%). In the PD-L1-positive subset, DCR-24w was highest in advanced cutaneous melanoma (n = 3, 66.7%), NSCLC (n = 86, 36.0%), HCC and bladder cancer (n = 3 each, 33.3% each), and SCCHN (n = 22, 18.2%).

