The populations included in Cohorts 3 and 4, who have had progression of disease during treatment with a checkpoint inhibitor, represent a potential unmet medical need. For this reason, if results in Stage 2 of enrollment are of high interest, enrollment may be expanded to as many as 100 patients total in each cohort to narrow the 95% Confidence Interval (CI) around the ORR point estimate and more fully characterize the secondary endpoints in the population of interest.

In order to be part of the clinical activity evaluable population, the patient must have at least one on-study disease assessment or discontinue from treatment for PD prior to this assessment. Patients who discontinue treatment prior to the first on-study disease assessment for an AE, toxicity, or withdraw consent are considered non-evaluable for disease assessment. These patients will not be part of the clinical activity evaluable population.

Disease response and progression as documented by the investigator in the CRF will be the basis for patient management and study expansion decision making. Unconfirmed objective responses recorded in the CRF may be used as the initial basis for expansion of study enrollment; however, follow-up evaluations on patients with unconfirmed responses must continue to support the decision to continue to the full number of patients to be included in the next stage. Central radiology review for disease response and progression may be added to the study during Stage 2. If this occurs, central review of all radiologic assessments performed in the study will be expected (including retrospective review of patients enrolled in Stage 1), and central radiology review for disease response will be the basis for the primary statistical analyses to estimate the objective response rate and its confidence interval, as well as the duration of response and PFS.

Study treatment will continue until disease progression, unacceptable adverse events, patient refusal or death.

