## **6.5 Patient Discontinuation/Withdrawal**

Patients may discontinue from study treatment or from the study at any time at their own request, or they may be discontinued at any time at the discretion of the investigator or Sponsor for safety, behavioral reasons, or the inability of the patient to comply with the protocol required schedule of study visits or procedures at a given study site.

Criteria that may be used to discontinue patients from receipt of study medication will include, but will not be limited to:

- Objective disease progression according to RECIST 1.1 as determined by the investigator (patients who may derive clinical benefit may continue on treatment at the discretion of the investigator);
- Global deterioration of health status requiring discontinuation;
- Adverse event;
- Significant protocol violation;
- Lost to follow-up;
- Refusal for further treatment;
- Study termination by Sponsor;
- Death.

Reasons for discontinuation from study follow-up may include:

- Study terminated by Sponsor;
- Lost to follow-up;
- Refusal for further follow-up for survival;
- Death.

If a patient does not return for a scheduled visit, every effort should be made to contact the patient. At least 2 attempts should be made to contact the patient, and each attempt should be recorded in the source documents. In any circumstance, every effort should be made to document patient outcome, if possible. The investigator should inquire about the

reason for withdrawal, request that the patient returns for a final visit, and if applicable, follow-up with the patient regarding any unresolved adverse events.

If the patient withdraws from the study treatment and also withdraws consent for disclosure of future information, no further evaluations should be performed, and no additional data should be collected. The Sponsor may retain and continue to use any data collected before such refusal for further follow-up.

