## 7.2 Efficacy

All patients enrolled in the study are to be evaluated for disease activity as outlined in the Schedule of Assessments (Table 1). Screening/baseline tumor assessments should include CT or MRI of the chest, abdomen, and pelvis, whole body bone scan, MRI of the brain and evaluation of any superficial lesions. On-study assessments will include all known and suspected sites of disease and will be performed at 8 week intervals until approximately 1-year and then every 12 weeks. The allowable windows for assessments are 4 weeks prior to first study treatment for screening/baseline assessments and  $\pm 10$  days for on-study disease assessments.

CT scans should be performed with contrast agents unless contraindicated for medical reasons. If intravenous contrast is medically contraindicated, the imaging modality to be used (either CT without contrast or MRI) should be the modality which best evaluates the disease, and the choice should be determined by the investigator in conjunction with the local radiologist. Depending on the adequacy for evaluation of disease, a combination of CT without contrast and MRI should most often be used. CT without contrast is preferred for evaluation of lesions in lung parenchyma. MRI is not adequate for evaluation of lung parenchyma but should also be performed to evaluate all other aspects of the chest. MRI of the abdomen and pelvis should substitute for CT with contrast unless the method does not adequately depict the individual's disease, in which case CT without contrast is preferred. For those sites that routinely use PET scans for assessment of bone lesions in lieu of skeletal scintigraphy, PET scans may be used on-study, with the same modality planned throughout the study for any given patient.

For patients having effusions or ascites, cytological proof of malignancy should be obtained prior to selection of the effusion as a non-target lesion. Effusions that have not been evaluated using cytology or were found to be non-malignant should not be considered to be cancer lesions.

Disease response will be assessed in accordance with RECIST 1.1 (Eisenhauer-2009). Appendix 5 provides guidance in using the response criteria and include a modification to RECIST 1.1 to address potential temporary treatment effects such as tumor lesion cavitation or flare response. Assessments will be performed until objective disease progression is documented by the investigator, or subsequent anti-cancer therapy is begun.

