***Subjective Progression***

Patients requiring discontinuation of treatment due to worsening health status attributable to advancement of the malignancy under study but without objective evidence of disease progression should not be reported as PD on tumor assessment CRFs. This should be indicated on the end of treatment CRF as off treatment due to Global Deterioration of Health Status.

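### As worded, the evaluable population leaves out patients who die, or stop for global deterioration, without any on-study scan, which biases the response rate used for the go rules upward

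*Protocol*

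**What the plan says.** Protocol 9.3.2 and SAP 7.3 say that an evaluable patient "must have at least one on-study disease assessment or discontinue from treatment for PD". Protocol 3.2 and SAP 6.2 say the same with a few words added at the end: "must have at least one on-study disease assessment or discontinue from treatment for PD prior to this assessment". A second sentence gives the exclusions: "Patients who discontinue treatment prior to the first on-study disease assessment for an AE, toxicity, or withdraw consent are considered non-evaluable". Death and global deterioration are not in that list.

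The protocol's abbreviation list expands PD as "Objective Progression of Disease". Protocol 6.5 lists "Global deterioration of health status requiring discontinuation", and also death, as reasons for stopping separate from objective progression. Appendix 5 (Subjective Progression) says that worsening health attributed to the cancer but "without objective evidence of disease progression should not be reported as PD on tumor assessment CRFs"; it goes on the end of treatment form instead.

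Disease is assessed every 8 weeks from Cycle 1 Day 1. Protocol 7.2 adds: "Assessments will be performed until objective disease progression is documented by the investigator, or subsequent anti-cancer therapy is begun".

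Both documents use the evaluable population for the Predictive Probability decisions, and the stage sizes (9 then 17; 17 then 44) count evaluable patients. SAP 12.5.1 also makes it the primary population for ORR, with mITT supportive. Protocol 9.3.1 makes mITT primary for efficacy and uses mITT for the decision to expand to 100 patients.

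For the durvalumab monotherapy data, Protocol 1.1.1 and 1.3.5 describe a response-evaluable set that includes patients with a follow-up scan "or discontinued due to disease progression or death without any follow-up scan".

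**The concern.** The patients at issue are treatment failures. A patient who dies in the first eight weeks of combination treatment, or declines too far to be scanned, cannot be a responder. If the definition puts that patient outside the denominator, enrollment continues until someone else fills the place, and the replacement has some chance of responding. The error therefore runs in one direction, toward a false go. SAP 12.5.1 counts patients who cannot be assessed as non-responders, but only within the population being analyzed, so it does not reach patients already outside it.

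What is at stake is the decision to continue each cohort at Stage 1, the decision that further investigation may be warranted, and the primary ORR if the SAP's choice of population stands. The trial is single-arm and has no data monitoring committee, so these decisions rest on a comparison with fixed null rates. That comparison is fair only if early failures are handled alike on both sides.

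The two sentences of the definition also collide. A patient who stops for toxicity at week 6 and is scanned at week 8, as Protocol 7.2 requires, has an on-study assessment and so qualifies under the first sentence. The same patient stopped for toxicity before the first assessment and so is excluded by the second.

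**Working it through.** **Who is in the set.**

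| Patient with no on-study scan who | Meets an entry condition? | Named as excluded? |
|---|---|---|
| stops for objective PD | yes | no |
| stops for AE or toxicity, or withdraws consent | no | yes |
| stops for global deterioration | no | no |
| dies | no | no |

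The last two rows are the gap. Read literally, the entry conditions keep these patients out.

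**Reproducing the stated error rates** (Protocol 9.1.2). With n1 patients and at least r1 responses needed at Stage 1, then n patients and at least r responses in total, the probability of a go at true rate p is

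Go(p) = Σ over x ≥ r1 of P[Bin(n1, p) = x] × P[Bin(n − n1, p) ≥ r − x].

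Cohorts 1, 3 and 4 (n1 = 9, r1 = 1, n = 17, r = 3) at p = 0.05:

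- early stop: 0.95^9 = 0.6302
- one response at Stage 1: 9 × 0.05 × 0.95^8 = 0.2985. At least 2 of 8 are then needed: 1 − 0.6634 − 0.2793 = 0.0572. Product 0.0171
- two responses: 36 × 0.05² × 0.95^7 = 0.0629. At least 1 of 8 is then needed: 0.3366. Product 0.0212
- three or more: 0.0084
- total: 0.0466, as stated. At p = 0.30 the same formula gives 0.9045, as stated.

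Cohort 2 (n1 = 17, r1 = 5, n = 44, r = 18) gives early stopping 0.4977 and Type 1 error 0.0303 at p = 0.27, and power 0.9018 at p = 0.50, all as stated. The design arithmetic is correct for response rates of 5% and 27% among evaluable patients.

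**Effect of dropping early failures.** Suppose that the null rate p0 holds on a denominator that keeps these patients, and that a fraction f of them is dropped. None of those dropped responded, so the null rate among evaluable patients becomes p0/(1 − f). The documents give no value for f; 5 to 20% is an assumed range.

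| f | Cohort 2: p0/(1 − f) | Type 1 error | Cohort 1 rule: p0/(1 − f) | Type 1 error |
|---|---|---|---|---|
| 0 | 0.270 | 0.030 | 0.050 | 0.047 |
| 5% | 0.284 | 0.049 | 0.053 | 0.053 |
| 10% | 0.300 | 0.078 | 0.056 | 0.060 |
| 15% | 0.318 | 0.123 | 0.059 | 0.069 |
| 20% | 0.338 | 0.190 | 0.063 | 0.080 |

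The limit of 0.05 set in Protocol 9.1.2 is reached at f of about 5.3% in Cohort 2 (one patient in 19) and about 2.8% under the Cohort 1 rule (one in 36).

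**Which denominator the null rates have.** The definition that keeps unscanned deaths is attached to 26.7% of 86 and 6.3% of 95 patients (Protocol 1.1.1; the first figure also in 1.3.5). The null rates of 27% and 5% match the figures in Protocol 1.5, 23 of 84 and 5 of 92, for which no evaluability definition is given. Sections 1.1.1 and 1.5 cite the same conference abstract, and 26.7% of 86 is also 23 responders, so a common definition is plausible but is not stated. For Cohorts 3 and 4 the 5% is simply assumed in Protocol 9.1.2, with no source.

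**The case against.** Several counter-arguments carry weight.

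- The definition is silent rather than explicit. The exclusion sentence does not name death or global deterioration, so one could argue that they were never meant to be excluded. But the entry conditions are stated as a requirement, and these patients do not meet them. Either reading needs a clarification, because this set decides go or no-go.
- A patient who stops for global deterioration should still be scanned under Protocol 7.2, and would then be evaluable. This stands. It limits the affected group to patients who die before any scan and those who deteriorate and never have one.
- The benchmark wording covers disease progression or death. Whether its progression includes clinical deterioration is not said. This stands; only the unscanned deaths are clearly treated differently.
- Eligibility requires ECOG 0 or 1, so f may be small. At 5%, Cohort 2 is still just inside the limit, at 0.049. This stands, and it is why the size can be given only as a range.
- A pass means only that further investigation may be warranted, and the stopping rules will be recalculated for the actual Stage 1 numbers. True, but recalculation on the same set does not remove the bias.

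A reader might infer that the trial's ORR is inflated without qualification, and that the go rules have been shown to lose their stated Type 1 error because the comparator counted these patients. The documents do not support that much. The protocol's mITT analysis keeps such patients once they have received both drugs. The link between the benchmark definition and the null rates is an inference. The fraction dropped is unknown.

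**Conclusion.** The gap in the definition is real, and the bias has a known direction. Unscanned deaths, and global deteriorations that are never scanned, leave the evaluable denominator and are replaced. This raises the response rate used for the Stage 1 and final go rules and, under SAP 12.5.1, the primary ORR. It does not touch the protocol's mITT primary ORR or the mITT-based decision to expand to 100 patients.

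The size is conditional. The inflated error rates in the table rest on two assumptions: that the null rates apply to a denominator that keeps these patients, and that f lies between 5 and 20%. The first has some textual support for Cohorts 1 and 2 and none for Cohorts 3 and 4. For those two cohorts the upward bias in the evaluable-set ORR remains, but a mismatch with a benchmark cannot be shown. Cohort 2 is the most sensitive over this range, although it starts with more room below 0.05.

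This should be corrected, but as a clarification of the population. It is not evidence that the stated operating characteristics are wrong on their own terms.

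**What to change.** In Protocol 3.2 and 9.3.2, SAP 6.2 and 7.3, and the protocol's Study Summary, add two statements:

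1. Treated patients who die, or who stop for global deterioration of health status, without any on-study scan are evaluable and count as non-responders.
2. Any post-baseline disease assessment makes a patient evaluable, even if treatment had stopped earlier for an adverse event or another reason.

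Patients with no scan who stopped for a non-fatal adverse event or toxicity, or who withdrew consent, would remain non-evaluable as now. With these patients counted, f is zero and the stated error rates of 0.0466 and 0.0303 apply on a denominator that keeps early failures.

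The cost is a short wording change in five places. Stop reasons, deaths and scan dates are already collected, and no visit or treatment changes. The downside is that the ORR in the evaluable set may come out slightly lower.
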